## PROTOCOL SYNOPSIS

**Gilead Sciences, Inc.**  
**[name]**  
**[name]**

---

Study Title:	A Phase 3, Randomized Double-Blind Placebo-Controlled Trial to Evaluate the Efficacy and Safety of Remdesivir (GS-5734™) Treatment of COVID-19 in an Outpatient Setting
IND Number:	147753
EudraCT Number:	2020-003510-12
Clinical Trials.gov Identifier:	NCT04501952
Study Centers Planned:	Approximately 150 centers globally
Objectives:	
The purpose of this trial is to evaluate treatment with intravenous (IV) administered remdesivir (RDV, GS-5734) in an outpatient setting in participants with confirmed coronavirus disease 2019 (COVID-19) who are at risk for disease progression.
 
The primary objectives of this study are as follows:
 

• To evaluate the efficacy of RDV in reducing the rate of COVID-19 related hospitalization or all-cause death in non-hospitalized participants with early stage COVID-19

• To evaluate the safety of RDV administered in an outpatient setting

 
The secondary objectives of this study are as follows:
 

• To evaluate the efficacy of RDV in reducing the rate of COVID-19 related medically attended visits (MAVs; medical visits attended in person by the participant and a health care professional) or all-cause death in non-hospitalized participants with early stage COVID-19

• To determine the antiviral activity of RDV on severe acute respiratory syndrome (SARS)-coronavirus (CoV)-2 viral load

• To assess the impact of RDV on symptom duration and severity

CCI

**Study Design:** This is a Phase 3, randomized, double-blind, placebo-controlled, multicenter study of RDV therapy for outpatients with early stage COVID-19 who are at higher risk of disease progression.

Participants who meet all eligibility criteria may be randomized in a 1:1 ratio to RDV or placebo. Randomization will be stratified by participants who reside in a skilled nursing facility, by participant's age (< 60 vs ≥ 60 years), and by region (United States [US] vs ex-US):

**Treatment Group A:** single dose of IV RDV 200 mg on Day 1 followed by IV RDV 100 mg on Days 2 and 3 (RDV group)

**Treatment Group B:** IV placebo-to-match (PTM) RDV on Days 1 to 3 (PTM group)

Number of Participants Planned: Approximately 1264 participants

Target Population: Non-hospitalized participants with early stage COVID-19 and at least one risk factor for disease progression.

Duration of Treatment: Participants will receive study treatment with RDV or PTM for 3 days

Diagnosis and Main Eligibility Criteria: Participants with COVID-19 who meet the following inclusion criteria may be included:

- Willing and able to provide written informed consent (age ≥18) or assent (age ≥12 to <18, where locally and nationally approved), or with a legal representative who can provide informed consent (where locally and nationally approved)

- Either:
  - At least 1 pre-existing risk factor for progression to hospitalization (chronic lung disease, hypertension, cardiovascular or cerebrovascular disease, diabetes, obesity (BMI  $\geq 30$ ), immunocompromised, chronic mild or moderate kidney disease, chronic liver disease, current cancer, or sickle cell disease);
  - OR age  $\geq 60$  years
- SARS-CoV-2 infection confirmed by molecular diagnostics (nucleic acid [eg, PCR] or antigen testing)  $\leq 4$  days prior to screening
- Presence of  $\geq 1$  symptom(s) consistent with COVID-19 for  $\leq 7$  days prior to randomization (such as fever, cough, fatigue, shortness of breath, sore throat, headache, myalgia/arthritis)
- Not currently receiving, requiring, or expected to require supplemental oxygen
- Not currently requiring hospitalization (hospitalization defined as  $\geq 24$  hours of acute care)

Exclusion criteria for participation include:

- Participation in any other clinical trial of an experimental treatment and prevention for COVID-19
- Prior hospitalization for COVID-19 (hospitalization defined as  $\geq 24$  hours of acute care)
- Treatment with other agents with actual or possible direct antiviral activity against SARS-CoV-2 or administration of any SARS-CoV-2 (or COVID-19) vaccine
- Known hypersensitivity to the study drug, metabolites, or formulation excipient

Study Procedures/  
Frequency:

At screening, after the participant has provided informed consent, demographic and baseline characteristics and medical history will be collected. Current clinical history, and concomitant medications will be documented. Physical examination findings, vital signs including temperature, respiratory rate, and SpO2 on room air will be documented. Women of childbearing potential will have a urine pregnancy test.

After screening procedures, eligible participants may be randomized in a 1:1 ratio to receive treatment with RDV or PTM.

Randomization will be stratified by residence in a skilled nursing facility, participant's age (<60 vs ≥ 60 years), and region (US vs ex-US).

After randomization, all participants randomized to receive RDV or PTM should receive their initial dose on Day 1.

Nasopharyngeal swabs and sputum samples will be collected on Days 1, 2, 3, 7, and 14 for SARS-CoV-2 quantitative reverse transcriptase polymerase chain reaction viral load testing and possible resistance testing.

On study Days 1 through 3, vital signs including respiratory status will be measured, and adverse events (AEs), medically attended visit information and concomitant medications will be documented. Laboratory tests for safety (hematology, chemistry, and coagulation) will be performed on Days 1, 3, 7, and 14. **CCI**

On study

Day 14 physical examination findings, vital signs including temperature, respiratory rate, and SpO2, AEs, medically attended visit information and concomitant medications will be documented.

Symptom severity will be assessed daily from Day 1 through Day 14 using the COVID-19-adapted FLU-PRO Plus questionnaire (if available).

On study Day 28, there will be an in-person or phone visit. Physical examination, vital signs including temperature, respiratory rate, and SpO2, AEs, medically attended visit information and concomitant medications will be documented (only AEs, medically attended visit information and concomitant medications needed if performed by phone).

**CCI**

A large rectangular area of the page is completely blacked out, indicating redacted content. The text "CCI" is printed in red at the top left corner of this redacted area.

---

Test Product, Dose, and Mode of Administration:	Remdesivir for injection, 100 mg, for IV administration
Reference Therapy, Dose, and Mode of Administration:	Placebo-to-Match
Criteria for Evaluation:	
The primary endpoints of this study are:
 

• Composite endpoint of COVID-19 related hospitalization (defined as at least 24 hours of acute care) or all-cause death by Day 28

• Proportion of participants with treatment-emergent AEs

 
The secondary endpoints of this study are:
 

• Composite endpoint of COVID-19 related MAVs (medical visits attended in person by the participant and a health care professional) or all-cause death by Day 28

• All-cause mortality at Day 28

• Proportion of participants hospitalized by Day 28

• Composite endpoint of COVID-19 related hospitalization (defined as at least 24 hours of acute care) or all-cause death by Day 14

• Composite endpoint of COVID-19 related MAVs (medical visits attended in person by the participant and a health care professional) or all-cause death by Day 14

• Time-weighted average change in SARS-CoV-2 viral load from baseline to Day 7

• Time to alleviation (mild or absent) of baseline COVID-19 symptoms as reported on the COVID-19-adapted FLU-PRO Plus

• Proportion of participants progressing to requiring oxygen supplementation by Day 28

CCI

[REDACTED]

[REDACTED]

[REDACTED]

[REDACTED]

[REDACTED]

[REDACTED]

**Statistical Methods:**

The total sample size of the study will be approximately 1264 participants.

A sample size of approximately 1264 participants (632 in each group with 1:1 randomization) achieves > 90% power to detect a ratio of 0.55 (RDV to placebo in proportion of COVID-19 related hospitalization or all-cause death rate, which is equal to a hazard ratio of 0.534) using a 2-sided significance level of 0.05 assuming the overall hospitalization or death rate is 9.3% (12% in the placebo group and 6.6% in the RDV group) and a 5% drop out rate. The sample size provides approximately 80% power to detect a ratio of 0.60 (RDV to placebo). This analysis will be stratified by residence in skilled nursing facility, age (<60 vs ≥60 years), and region (US vs ex-US). An unblinded sample size re-estimation is planned after 50% participants completed Day 28.

The primary endpoint will be analyzed using Cox model with stratification factors as covariates. The null hypothesis being tested is whether the ratio of hospitalization or death is the same for either RDV or placebo treatment. The ratio and 95% confidence interval will be provided.

Treatment-emergent AEs and laboratory abnormalities will be summarized using descriptive statistics and listed by participant.

---

This study will be conducted in accordance with the guidelines of Good Clinical Practice including archiving of essential documents.

## **GLOSSARY OF ABBREVIATIONS AND DEFINITION OF TERMS**

AE	adverse event
ALT	alanine aminotransferase
aPTT	activated partial thromboplastin time
ARDS	acute respiratory distress syndrome
AST	aspartate aminotransferase
ATP	adenosine triphosphate
CI	confidence interval
CL cr	creatinine clearance
CoV	coronavirus
COVID-19	coronavirus disease 2019
CP	conditional power
CRF	case report form
DAIDS	Division of AIDS
DMC	data monitoring committee
eCCGs	eCRF completion guidelines
eCRF	electronic case report form
EDC	electronic data capture
eGFR	estimated glomerular filtration rate
eSAE	electronic serious adverse event
EU	European Union
FDA	Food and Drug Administration
FLU-PRO Plus ®	InFLUenza Patient-Reported Outcome Plus
GCP	Good Clinical Practice
Gilead	Gilead Sciences, Inc.
GLPS	Global Patient Safety
HIV	human immunodeficiency virus
IB	investigator's brochure
ICH	International Council for Harmonisation (of Technical Requirements for Pharmaceuticals for Human Use)
IDMC	independent data monitoring committee
IEC	independent ethics committee
IND	investigational new drug
INR	international normalized ratio
IRB	institutional review board
IV	intravenous
IXRS	interactive voice/web response system
LLOQ	lower limit of quantitation
MAV	medically attended visit
O 2	oxygen

---

PCR	polymerase chain reaction
PI	principal investigator
PK	pharmacokinetic(s)
PT	prothrombin time
PTM	placebo-to-match
qRT-PCR	quantitative reverse transcriptase polymerase chain reaction
RDV	remdesivir (GS-5734 TM )
RNA	ribonucleic acid
SAE	serious adverse event
SARS	severe acute respiratory syndrome
SBECD	sulfobutylether $\beta$ -cyclodextrin sodium
SDV	source data verification
SOC	standard of care
SOP	standard operating procedure
SpO 2	oxygen saturation
SUSAR	suspected unexpected serious adverse reaction
ULN	upper limit of normal
US	United States

## 1. INTRODUCTION

### 1.1. Background

Severe acute respiratory syndrome (SARS)-coronavirus (CoV)-2, a single-stranded RNA virus, is identified as the cause of an outbreak of respiratory illness that was first detected in Wuhan, China in December 2019. The virus has now spread globally, resulting in a global pandemic and causing severe respiratory illness throughout the world. Severe cases progress to pneumonia and multi-organ failure, which can lead to death. Gilead Sciences, Inc. (Gilead) has been working with global health authorities to respond to the ongoing pandemic and to evaluate the utility of intravenous (IV) remdesivir (RDV; GS-5734TM) as a treatment option for coronavirus disease 2019 (COVID-19) through clinical trials. Remdesivir is approved for the treatment of COVID-19 in the United States (US), European Union (EU), Japan, and other countries for populations including adults and pediatric patients (12 years and older and weighing at least 40 kg).

### 1.2. Remdesivir (RDV, GS-5734)

Remdesivir is being developed by Gilead and is formulated for IV administration.

#### 1.2.1. General Information

Remdesivir is an adenosine nucleotide prodrug that distributes into cells where it is metabolized to form the pharmacologically active nucleoside triphosphate metabolite. Metabolism of remdesivir to remdesivir triphosphate has been demonstrated in multiple cell types. Remdesivir triphosphate acts as an analog of adenosine triphosphate (ATP) and competes with the natural ATP substrate for incorporation into nascent RNA chains by the SARS-CoV-2 RNA-dependent RNA polymerase, which results in delayed chain termination during replication of the viral RNA.

For further information on RDV, refer to the investigator's brochure (IB) for RDV.

### 1.3. Rationale for This Study

Remdesivir is a novel antiviral drug that exhibits potent nanomolar antiviral activity against SARS-CoV-2 in primary human airway epithelial cells {[Sheahan 2017](#)}. In SARS-CoV-2-infected rhesus monkeys, administration of RDV resulted in a significant reduction in clinical signs of respiratory disease, lung pathology and gross lung lesions, and viral RNA levels compared with vehicle-treated animals {[Williamson 2020](#)}. The safety and efficacy of RDV has been demonstrated in clinical studies of patients hospitalized with COVID-19.

The risk of adverse outcomes from COVID-19 increases with age and the presence of chronic health conditions, such as cardiovascular disease, diabetes, and chronic lung disease {[Stokes 2020, The Novel Coronavirus Pneumonia Emergency Response Epidemiology Team 2020, World Health Organization \(WHO\) 2020a](#)}. In acute viral infection with influenza, a short course of antiviral treatment has shown improved clinical outcome {[Nicholson 2000](#)}. Treatment intervention in the earlier phase of COVID-19, such as in an outpatient setting, may prevent disease progression to moderate disease requiring hospitalization. The resulting reduction in hospitalizations would significantly benefit patients and would reduce the burden to health care systems.

There is currently no approved treatment for patients with COVID-19 who have not been hospitalized. This study will evaluate the potential for a 3-day treatment with IV RDV to change the clinical trajectory of early COVID-19. The double blinded design will allow stringent evaluation of the safety and efficacy of RDV in this population.

Participants in this study will be treated with RDV for a maximum of 3 days receiving a total of 400 mg RDV. This dose corresponds to a total administration of 12 g of sulfobutylether β-cyclodextrin sodium (SBEDC) using the lyophilized powder. Based on the European Medicines Agency (EMA) review summarizing the safety of cyclodextrins as excipients {[Committee for Medicinal Products for Human Use \(CHMP\) 2014](#)}, which indicates approximately 250 mg/kg/day of SBEDC (12 g/day based on a 48 kg human) is safe, participants will not be required to discontinue RDV if their creatinine clearance is < 30 mL/min during the dosing period.

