#### **1.5. Rationale for Dose Selection of Remdesivir**

The dosing of RDV in this study, 200 mg on Day 1 and 100 mg on each of Days 2 and 3 is the initial dosing recommended by US Food and Drug Administration (FDA) and approved by EMA for adults and adolescents weighing ≥ 40 kg.

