## **6.8. Criteria for Discontinuation of Study Treatment**

Study medication will be discontinued for individual participants in the following instances, unless the potential for resuming dosing is specifically noted:

- Intercurrent illness that would, in the judgment of the investigator, affect assessments of clinical status to a significant degree. Following resolution of intercurrent illness, the participant may resume study dosing at the discretion of the investigator.
- Unacceptable toxicity, or toxicity that, in the judgment of the investigator, compromises the ability to continue study-specific procedures or is considered to not be in the participant's best interest
- ALT or AST  $\geq 5 \times$  ULN; or ALT  $> 3 \times$  ULN and total bilirubin  $> 2 \times$  ULN, confirmed by immediate repeat testing
- Other Grade 3 or Grade 4 abnormal laboratory results related to RDV
- Lack of efficacy
- Participant request to discontinue for any reason
- Participant noncompliance
- Discontinuation of the study at the request of Gilead, a regulatory agency or an IRB or IEC
- Infusion-related systemic reaction  $\geq$  Grade 2 or infusion-related localized reaction  $\geq$  Grade 3

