### **8.6.3. Laboratory Evaluations**

Selected laboratory data will be summarized using only observed data. Data and change from baseline at all scheduled time points will be summarized.

Graded laboratory abnormalities will be defined using the grading scheme in DAIDS Table for Grading the Severity of Adult and Pediatric Adverse Events, Version 2.1 dated July 2017.

Incidence of treatment-emergent laboratory abnormalities, defined as values that increase at least 1 toxicity grade from baseline at any time post baseline up to the end date of the study, will be summarized by treatment group. If baseline data are missing, then any graded abnormality (ie, at least a Grade 1) will be considered treatment-emergent.

Laboratory abnormalities that occur before the first dose of study drug or after the participant has been discontinued from treatment for more than 30 days will be included in a data listing.

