	Lymphocytes	Decrease	Lymphocytes (Decreased)
	Neutrophils	Decrease	Neutrophils (Decreased)
	Platelets	Decrease	Platelets (Decreased)
	WBC	Decrease	WBC (Decreased)
Chemistry	Albumin	Decrease	Albumin (Decreased)
	Alkaline Phosphatase	Increase	Alkaline Phosphatase (Increased)
	ALT	Increase	ALT (Increased)
	AST	Increase	AST (Increased)
	Bicarbonate	Decrease	Bicarbonate (Decreased)
	Corrected Calcium	Increase	Corrected Calcium (Hypercalcemia)
	Corrected Calcium	Decrease	Corrected Calcium (Hypocalcemia)
	Creatine Kinase (CK)	Increase	Creatine Kinase (Increased)
	Creatinine	Increase	Creatinine (Increased)
	Creatinine Clearance	Decrease	Creatinine Clearance (Decreased)
	Lipase	Increase	Lipase (Increased)
	Magnesium	Decrease	Magnesium (Hypomagnesemia)
	Phosphate	Decrease	Phosphate (Hypophosphatemia)
	Serum Glucose (Fasting)	Increase	Serum Glucose (Fasting, Hyperglycemia)
Coagulation	Serum Glucose (Nonfasting)	Increase	Serum Glucose (Nonfasting, Hyperglycemia)
	Serum Glucose	Decrease	Serum Glucose (Hypoglycemia)
	Serum Potassium	Increase	Serum Potassium (Hyperkalemia)
	Serum Potassium	Decrease	Serum Potassium (Hypokalemia)
	Serum Sodium	Increase	Serum Sodium (Hypernatremia)
	Serum Sodium	Decrease	Serum Sodium (Hyponatremia)
	Total Bilirubin	Increase	Total Bilirubin (Hyperbilirubinemia)
	Uric Acid	Increase	Uric Acid (Hyperuricemia)
	Prothrombin Intl. Normalized Ratio (INR)	Increase	Prothrombin Intl. Normalized Ratio (Increased)
	Activated partial thromboplastin time (aPTT)	Increase	Activated partial thromboplastin time (Increased)

15) SAS code for ANCOVA:

```

ods output ParameterEstimates=out1 LSMeans=out2 LSMeanCL=out3
LSMeanDiffCL=out4;
proc glm data=dat1 plots=none;
class trt01pn;
model DAVG = trt01pn base / solution;
lsmeans trt01pn / stderr cl pdiff;
run;

```

```
ods output close; quit;
```

16) Symptom scores in the FLU-PRO questionnaire raw data start from 1 to n (total number of responses in a question), in the FLU-PRO user manual, symptom scores start from 0. In the analysis dataset, symptom scores will be re-mapped to match the scoring in the FLU-PRO user manual for proper calculation of total score and domain score.

17) FLU-PRO Total Score and Domain Score:

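### Protocol 1.3 and 6.8 disagree on stopping study drug for creatinine clearance below 30 mL/min, if that result is Grade 3 or 4 and judged related to RDV

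*Protocol*

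**What the plan says.** Protocol 1.3 (Rationale for This Study) ends with a statement about renal function during treatment: "participants will not be required to discontinue RDV if their creatinine clearance is < 30 mL/min during the dosing period". The support given is an excipient argument, which sets the amount of cyclodextrin in the course beside a daily amount described as safe.

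Protocol 6.8 (Criteria for Discontinuation of Study Treatment) opens with "Study medication will be discontinued for individual participants in the following instances, unless the potential for resuming dosing is specifically noted". After a criterion for liver tests it lists "Other Grade 3 or Grade 4 abnormal laboratory results related to RDV". No resumption is noted for that criterion, creatinine clearance is not excepted, and 1.3 is not mentioned. Section 6.8 also has no criterion based on a clearance of 30 mL/min as such.

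On grading, Protocol 8.6.3 says "Graded laboratory abnormalities will be defined using the grading scheme in DAIDS Table for Grading the Severity of Adult and Pediatric Adverse Events", Version 2.1. SAP 7.2.2 uses the same scale. SAP Appendix 2, item 14, lists decreased creatinine clearance and increased creatinine among the graded chemistry tests. Neither document prints the grade cut-offs.

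**The concern.** A site that sees a clearance below 30 mL/min during dosing has two statements to consult. The one in the rationale says stopping is not required. The one in the operative list may say that study drug will be stopped. If both apply to the same result, sites can handle the same renal event differently while each follows the protocol as it read it.

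This bears on participant safety and on the safety tables:

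- SAP 4.1 summarises premature discontinuation of study drug, with reasons.
- SAP 7.1.7 summarises treatment-emergent adverse events that caused premature discontinuation of study drug.
- Protocol 7.5 requires a laboratory abnormality that leads to discontinuation to be recorded as an adverse event, whereas one without clinical significance is not recorded. The decision to stop can therefore determine whether an event is recorded at all.

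**Working it through.** **1. When the two sections meet.** The 6.8 criterion needs two things that 1.3 does not mention: a Grade 3 or 4 result, and a judgement that it is related to RDV. The cut-offs are not in the documents, so both cases are shown for a clearance below 30 mL/min during dosing.

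| Grade of the result (assumption) | Judged related to RDV | Section 1.3 | This 6.8 criterion | Result |
|---|---|---|---|---|
| 3 or 4 | Yes | Stopping not required | Stop | Conflict |
| 3 or 4 | No | Stopping not required | Not triggered | No conflict |
| 2 or lower | Either | Stopping not required | Not triggered | No conflict |

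Only the first row is a contradiction. On relatedness, Protocol 7.2.1 asks for evidence of another cause before answering no, and a reasonable possibility is enough for yes. A decline first seen during dosing could therefore meet the condition.

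**2. How many infusions are at stake.** Protocol 6.7.2 schedules renal function during dosing on Days 1 and 3. Protocol 6.3 lists the blood samples among the assessments to be completed before study drug is given.

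- Day 1 sample: taken before any exposure, so a low value cannot be related to RDV and this criterion is not triggered.
- Day 3 sample: taken after two infusions and before the third. This is the only scheduled sample in the dosing period that can produce the conflict.

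Infusions normally affected: 3 − 2 = 1. In the RDV group that is 100 mg of the 400 mg course (100/400 = 25%). Laboratory turnaround is not stated, so the third infusion may already have been given when the result arrives. An unscheduled test could bring the conflict forward.

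**3. The excipient figures behind 1.3.** The limit reproduces: 250 mg/kg/day × 48 kg = 12,000 mg/day = 12 g/day. The vial content of excipient is not printed, so the 12 g course total is taken as given.

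- Implied ratio: 12 g / 400 mg = 3 g per 100 mg of RDV.
- Daily amounts on the 200/100/100 mg schedule (Protocol 5.3): 6 g, 3 g and 3 g, which sum to 12 g.
- At 48 kg: 6,000/48 = 125 mg/kg on Day 1, and 125/250 = 50% of the cited limit. Days 2 and 3: 3,000/48 = 62.5 mg/kg, or 25%.
- At 40 kg (the adolescent minimum in Protocol 4.2): the limit is 250 × 40 = 10 g/day. Day 1 is 6,000/40 = 150 mg/kg, or 60%. Days 2 and 3 are 75 mg/kg, or 30%.
- Weight at which Day 1 would equal the limit: 6,000/250 = 24 kg.

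**The case against.** The best defence is that the sections have different scopes. Section 1.3 argues from the excipient, so it can be read as saying only that a low clearance does not in itself oblige stopping. Section 6.8 is consistent with that, because it sets no clearance threshold and acts only on Grade 3 or 4 results attributed to RDV. The wording in 1.3 is also permissive and sits in a rationale, so a site that stops under 6.8 breaches nothing in 1.3.

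Much of this stands, and it is why the point is conditional and narrow. It does not remove the point, because 1.3 states its conclusion without limiting it to the excipient or to unrelated results. A site that relies on 1.3 and continues after a related Grade 3 or 4 result acts against 6.8, and neither section says which prevails.

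A reader might go further and infer that the excipient argument is itself wrong: 12 g is set against 12 g/day, which looks like no margin, and 12 g would exceed the 10 g/day limit at 40 kg. The documents do not support that. Section 1.3 labels its figure as a course total ("This dose corresponds to a total administration of 12 g of sulfobutylether") for participants "treated with RDV for a maximum of 3 days receiving a total of 400 mg RDV", and labels the limit as daily. No participant is scheduled to receive 12 g in a day. Like for like, the largest daily amount is 6 g, so putting both figures on a daily basis widens the margin and leaves the conclusion of 1.3 unchanged.

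**Conclusion.** The point holds in a limited form. Sections 1.3 and 6.8 give opposite instructions for a creatinine clearance below 30 mL/min during dosing if that result is Grade 3 or 4 and is judged related to RDV. The grade is an assumption, since the cut-offs are not printed. If the grade is 2 or lower, there is no conflict through this criterion.

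On scheduled sampling the disagreement normally concerns only the third infusion. It can affect the counts of drug discontinuation and of adverse events leading to discontinuation. The documents give no frequency for such renal events, so the size of that effect cannot be estimated. Sample size, power and alpha are not affected. Taking the cited daily limit at face value, the excipient comparison is not an error that changes anything (Day 1 is 50% of the limit at 48 kg and 60% at 40 kg), and it forms no part of the point.

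**What to change.** Reconcile Protocol 1.3 and 6.8 so that a single rule for creatinine clearance below 30 mL/min during dosing governs, and state it in 6.8, where a site will look when deciding whether to stop. The text should make clear how that rule relates to the criterion for related Grade 3 or 4 laboratory results. Which rule applies is for the sponsor to decide.

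The cost is about one clause in 6.8, with matching wording or a cross-reference in 1.3. No new procedure, sample or analysis is needed.
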